For Trial A, intervention content will be delivered to participants via text messages from the WayToHealth platform. Penn Medicine and Geisinger will provide the patient data and appointment data needed for WayToHealth to deliver the interventions. This may include a unique identifier, medical record number, first and last name, address, appointment date, appointment time, appointment type, practice and physician information, patient town and zip code, date of birth, gender, phone number(s), documented allergy to the flu shot, and documentation of flu shot receipt for the 2020 flu season. Penn Medicine and Geisinger will also indicate which phone numbers have opted out of receiving text message reminders. WayToHealth will receive these data from Penn Medicine via a secure data feed and from Geisinger via a secure upload. There will be data use agreements in place governing the data sharing with WayToHealth and Wharton as required. The Penn Medicine Academic Computing Services (PMACS) will be the hub for the hardware and database infrastructure that will support the project and is where the WayToHealth web portal is based. The PMACS is a joint effort of the University of Pennsylvania's Abramson Cancer Center, the Cardiovascular Institute, the Department of Pathology, and the Leonard Davis Institute. The PMACS provides a secure computing environment for a large volume of highly sensitive data, including clinical, genetic, socioeconomic, and financial information. Among the IT projects currently managed by PMACS are: (1) the capture and organization of complex, longitudinal clinical data via web and clinical applications portals from cancer patients enrolled in clinical trials; (2) the integration of genetic array databases and clinical data obtained from patients with cardiovascular disease; (3) computational biology and cytometry database management and analyses; (4) economic and health policy research using Medicare claims from over 40 million Medicare beneficiaries. PMACS requires all users of data or applications on PMACS servers to complete a PMACS-hosted cybersecurity awareness course annually, which stresses federal data security policies under data use agreements with the university. After the end of the intervention, patient and intervention data will be transferred from WayToHealth, Penn Medicine, and Geisinger to the Leonard Davis Institute's Health Services Research Data Center (HSRDC), which is maintained at a high security level in accordance with federal regulations (e.g., HIPAA) governing secure computer systems. This will include all data used for study implementation (i.e., the full list included above), as well as additional data to be used in analysis. The additional data may include patient diagnosis, procedures, and prescription information from the previous 5 years, marital status, and whether they have children, race/ethnicity, Charlson Comorbidity score, insurance type, a record of previous flu vaccinations from the previous 5 years, a record of all doctor visits in the past year, appointment arrival time, preferred pharmacy, number of emergency contacts and relation to emergency contacts, patient body mass index, smoking status, record of prior positive test for the flu, and primary care physician (PCP) specialty. Storage and analysis protocols for the data on the LDI HSRDC will be included in the data use agreement with Geisinger and Walmart. All identifiable data will be removed from this list as soon as possible, and will not be used for analysis. The Geisinger investigators will have access to data on (1) any intervention(s) they design, and (2) intervention data for Geisinger patients across all interventions for the purpose of running internal analyses through the HSRDC. They will handle all data in accordance with Geisinger and IRB policies. For Trial B, Walmart pharmacy will deliver the interventions directly to eligible Walmart pharmacy customers via their own text messaging platform. At the end of the intervention, Walmart pharmacy will transfer intervention data (e.g., to which intervention each customer was assigned, text messages sent and received) along with customer pharmacy and medical data (e.g., whether they received a flu shot, previous medical diagnoses) and customer demographic data (e.g., age, gender) to the HSRDC for analysis. Identifiable data will not be shared. For both Trial A and Trial B, collaborators at Penn and other institutions will access and analyze the non-identifiable data on participants assigned to the interventions they designed through the HSRDC. The server does not allow data to be copied or moved off of the server. Access will only be granted to investigators at other institutions after a data use agreement with Penn has been executed.

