Primary outcome variable(s)

Trial A: The primary outcome is whether participants receive a flu vaccination at their primary care appointment. Trial B: The primary outcome is whether participants receive a flu vaccination at any time in the fall of 2020 at a Walmart pharmacy.

Secondary outcome variable(s)

Trial A: A secondary outcome is whether participants receive a flu vaccination after their primary care appointment until March 31, 2021, after receiving the intervention. Trial B: A secondary outcome is whether participants receive a flu vaccination in the before March 31, 2021.

Background

Annually, the influenza causes millions of illnesses, hundreds of thousands of hospitalizations, and tens of thousands of deaths in the United States (CDC, 2020). The most effective way to combat the flu is with an annual vaccine, which can reduce the risk of contracting the flu by 50% and the risk of hospitalization by 80% (Thompson et al, 2018). The CDC recommends that everyone over 6-months old gets an annual flu vaccination, and estimates that in the 2017-2018 flu season alone (i.e., September 2017-March 2018), the flu vaccine prevented over six million illnesses, almost 100,000 hospitalizations, and almost 6,000 deaths (CDC, 2019). Despite these benefits, each year, less than half of Americans get a flu shot (CDC, 2019), leading to unnecessary illnesses. It is estimated that a 5% increase in vaccination rates in 2017-18 would have led to as many as 25,000 fewer hospitalizations (Hughes et al, 2019).

Study Design

Phase*

Not applicable

Design

Participants will be randomly assigned to the different study conditions. Randomization may be stratified by age, clinical site, primary care provider role, and other factors. Care providers will not be aware of the intervention received by the participant.

Study duration

Trial A: Penn Medicine and Geisinger Health patients with primary care appointments from September 1, 2020 to March 31, 2021 will be included. These participants may receive intervention messages up to four days prior to their scheduled appointments. In some conditions, participants will receive additional communications after their appointment about incentives they earned. Trial B: Walmart pharmacy customers will be assigned to an intervention and may receive intervention messages over the course of 4 days at the start of the flu season. They may also receive additional messages about incentives earned after receiving a flu shot.

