Resources necessary for human research protection

Describe research staff and justify that the staff are adequate in number and qualifications to conduct the research. Describe how you will ensure that all staff assisting with the research are adequately informed about the protocol and their research related duties. Please allow adequate time for the researchers to conduct and complete the research. Please confirm that there are adequate facilities for the research.

Penn Medicine, Geisinger, Walmart, and WayToHealth routinely collect and use the data that will be used in this study in the course of their normal business operations. They also routinely send patients text messages and encourage flu vaccinations. Research staff have completed necessary human research protection training.

Characteristics of the Study Population

Target population

Trial A: Adult patients with routine (i.e., non-sick) primary care appointments at Penn Medicine and Geisinger during the 2020-2021 flu season will be included. Trial B: Walmart pharmacy customers who consented to receive text messages and have received a flu vaccine at Walmart in the past will be included.

Subjects enrolled by Penn Researchers

80000

Subjects enrolled by Collaborating Researchers

1275000

Accrual

Penn Medicine, Geisinger Health, and Walmart will provide patient and appointment information to WayToHealth to include patients in the research if they are eligible. The estimated sample (i.e., 80,000 Penn Medicine patients, 75,000 Geisinger patients, and 1 million Walmart pharmacy customers) is based on the number of appointments meeting the eligibility criteria during the 2019-2020 flu season at Penn Medicine and Geisinger and the number of Walmart pharmacy customers who have consented to receive messages about their prescriptions, received a flu shot at Walmart in the past and been selected for the study by Walmart. We will include at least 4,000 participants in each condition, giving us at least 80% power to detect a 3% difference in vaccination rates across conditions.

Key inclusion criteria

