For both trials, the primary outcome will be whether participants receive an influenza vaccination, as recorded in their medical records or customer data. For Trial A, this will include whether they tell their provider they received a vaccination prior to their appointment but after enrollment in our study, receive a vaccination at their appointment, or receive their vaccination at another appointment or location after enrollment in our study (if documented in their medical record). For Trial B, this will include whether they receive the flu shot at a Walmart pharmacy after enrollment in our study. We will use an ordinary least squares (OLS) regression of a binary vaccination receipt indicator at the individual level, adjusting for individual characteristics (e.g., demographics, comorbidities), and visit characteristics (e.g., doctor information, clinic site; Trial A only).

The following documents are currently attached to this item:

There are no documents attached for this item.

Data confidentiality

Paper-based records will be kept in a secure location and only be accessible to personnel involved in the study.

- x **Computer-based files will only be made available to personnel involved in the study through the use of access privileges and passwords.**

Prior to access to any study-related information, personnel will be required to sign statements agreeing to protect the security and confidentiality of identifiable information.

- x **Wherever feasible, identifiers will be removed from study-related information.**

A Certificate of Confidentiality will be obtained, because the research could place the subject at risk of criminal or civil liability or cause damage to the subject's financial standing, employability, or liability.

A waiver of documentation of consent is being requested, because the only link between the subject and the study would be the consent document and the primary risk is a breach of confidentiality. (This is not an option for FDA-regulated research.)

- x **Precautions are in place to ensure the data is secure by using passwords and encryption, because the research involves web-based surveys.**

Audio and/or video recordings will be transcribed and then destroyed to eliminate audible identification of subjects.

Subject Confidentiality

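### Does the primary regression leave out prior flu-vaccination history and so give up the precision needed for the stated 80% power?

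*Protocol*

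**What the plan says.** The Analysis Plan section of the Protocol regresses a binary vaccination indicator by ordinary least squares at the individual level, "adjusting for individual characteristics (e.g., demographics, comorbidities), and visit characteristics (e.g., doctor information, clinic site; Trial A only"). No closed covariate list is given.

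The Data Management section describes additional Trial A data that may be transferred for use in analysis. Among them are "a record of previous flu vaccinations from the previous 5 years" and "appointment arrival time".

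The Design section says: "Randomization may be stratified by age, clinical site, primary care provider role, and other factors".

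The Accrual section sets a minimum size: "We will include at least 4,000 participants in each condition". It describes that minimum as "giving us at least 80% power to detect a 3% difference in vaccination rates across conditions". It states no alpha, sidedness, base rate or covariate R-squared.

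For Trial B, a past Walmart flu shot is an inclusion criterion, and no year-by-year history is listed for transfer.

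**The concern.** A participant's own past vaccination is an earlier value of the outcome, and adjusting for an earlier value of the outcome is usually a cheap way to gain precision. Here the data would be in hand for Trial A, yet the Analysis Plan mentions only demographics, comorbidities, doctor information and clinic site. If many conditions sat near 4,000 and the base rate were near one half, an unadjusted comparison would fall a few points short of 80% power, and a useful covariate could make up the difference.

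Two related worries follow. If randomisation strata were left out of the model, standard errors would be conservative. And the data list includes arrival time, which exists only for patients who attend and arises after randomisation. Used as a covariate, it would drop non-attenders, whose vaccinations elsewhere the Analysis Plan counts, and would condition on something the messages might affect.

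**Working it through.** **1. The stated power.** Inputs from the Protocol: n = 4,000 per condition and a difference of 0.03, read as percentage points. Assumed because not stated: two-sided alpha 0.05, two conditions of equal size, base rate p1 over a range. With p2 = p1 + 0.03,

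SE = sqrt{[p1(1 − p1) + p2(1 − p2)](1 − R²)/n}, power = Φ(0.03/SE − 1.960).

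At p1 = 0.45 and R² = 0: SE = sqrt[(0.2475 + 0.2496)/4,000] = 0.01115, 0.03/SE = 2.691, power = Φ(0.731) = 76.8%.

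| Base rate | Power, no adjustment |
|---|---|
| 25% | 86.0% |
| 30% | 82.4% |
| 35% | 79.6% |
| 40% | 77.8% |
| 45% | 76.8% |
| 48.5% (worst) | 76.6% |

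Power is at least 80% up to a base rate of about 34%. With a one-sided 0.05 test it is at least 85% at every base rate tried from 10% to 50%. The stated figure is therefore attainable without covariates under some readings and about 3.5 points short under the least favourable two-sided one. The Protocol does not say which reading applies.

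**2. What adjustment could add.** At p1 = 0.45, with R² assumed:

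| Total R² | Power | Equivalent sample, 1/(1 − R²) |
|---|---|---|
| 0 | 76.8% | 1.00 |
| 0.10 | 81.0% | 1.11 |
| 0.15 | 83.1% | 1.18 |
| 0.20 | 85.3% | 1.25 |
| 0.30 | 89.6% | 1.43 |

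These figures are right, but the R² = 0 row is not the planned analysis, because the plan already adjusts. The contribution of vaccination history is the increment over the other covariates. For illustration, if those gave 0.10 and history raised the total to 0.20, power would go from 81.0% to 85.3%. The sample equivalent would be 0.90/0.80 = 1.125, or 12.5% more participants, not 25%.

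**3. R² needed for exactly 80%.** R² = 1 − 4,000 × (0.03/2.802)²/[p1(1 − p1) + p2(1 − p2)]. This gives about 0.055 at a 40% base rate, 0.077 at 45% and 0.082 at 48.5%. None is needed at 30%. It is a total R², and nothing in the Protocol shows that the named covariates fall below it.

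**4. Trial B.** The Abstract expects about 1.2 million customers and the Accrual section 1 million. Suppose all 40 conditions sat in Trial B in equal arms: 30,000 or 25,000 per arm. At the worst base rate, 48.5%, with 25,000: SE = sqrt(0.49955/25,000) = 0.00447, 0.03/SE = 6.71, power = Φ(4.75), above 99.9%. Precision is not scarce there. The basic history indicator, any past Walmart shot, is also the same for everyone by eligibility.

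**5. Is history left out?** Each covariate list in the Analysis Plan opens with an e.g., so neither is exhaustive. A vaccination record fits within individual characteristics, and Data Management lists it as data for analysis. No sentence excludes it.

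**6. Strata.** The Design section names three possible factors. Age falls under demographics, clinical site under clinic site, and provider role most naturally under doctor information. Stratification is itself permissive and also allows unnamed factors, so the Protocol contains no final strata to compare with the model.

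**7. Arrival time.** It appears only in the data list. The visit characteristics given as examples, doctor and clinic, are known from the scheduled appointment. The data also serve the planned subgroup and machine-learning work, so presence on the list does not make an item a covariate. Nor can the list be read as putting arrival time into the model while keeping vaccination history out.

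**The case for a change.** The strongest case is that open wording cuts both ways. A list of examples over a large pool of data permits a poor covariate as readily as a good one. Visit characteristics carry no timing limit, and the five-year history has no stated index date although the data are transferred after the intervention ends. Trial A is also where precision counts: the Abstract lowers expected enrolment from 155,000 (80,000 + 75,000) to 125,600. The gain needs no shortfall either, since at a 30% base rate an R² of 0.10 lifts power from 82.4% to 86.1%.

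The arithmetic stands, and so does the principle that only values fixed before randomisation belong in the model. But these are specifications that a SAP commonly supplies, and the Protocol states nothing contrary to them. Lower Trial A enrolment does not change the calculation, because it already uses the 4,000 minimum, which the Accrual section presents as a floor. That demographics and comorbidities predict weakly and vaccination history strongly may well be true, but the Protocol has no figure for either.

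**Conclusion.** The concern does not hold. The Protocol neither omits prior vaccination from the model nor commits to a post-randomisation covariate. It gives examples and leaves the exact set open, as protocols commonly do. A need to restore 80% power would require a two-sided 5% test, a base rate above about 34%, and named covariates explaining less than roughly 5% to 8% of the outcome variance at base rates of 40% to 48.5%. None of these is in the document. Even then the gap is at most about 3.5 points in an unadjusted analysis that the plan does not use, and Trial B is unaffected. Naming vaccination history in the adjustment set would be sensible for precision in Trial A, but leaving it unnamed here produces no wrong result. The conclusion rests on reading the 3% as percentage points and on equal-sized conditions.
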